9.0 Data and Safety Monitoring Plan

This section is required when research involves more than Minimal Risk to subjects as defined in "HRP-001 SOP- Definitions."

Minimal Risk is defined as the probability and magnitude of harm or discomfort anticipated in the research that are not greater in and of themselves than those ordinarily encountered in daily life or during the performance of routine physical or psychological examinations or tests. For research involving prisoners, Minimal Risk is the probability and magnitude of physical or psychological harm that is normally encountered in the daily lives, or in the routine medical, dental, or psychological examination of healthy persons.

Please complete the sections below if the research involves more than minimal risk to subjects, otherwise indicate each section as not applicable.

[Do not type here]

9.1 Periodic evaluation of data

Describe the plan to periodically evaluate the data collected regarding both harms and benefits to determine whether subjects remain safe.

This clinical trial will be monitored with the assistance of the Data Management Unit at Penn State Health College of Medicine. Once weekly, the principal investigator and members of the study team will review results of liver function screens, pregnancy tests, vital signs, and results of the Columbia Suicide Severity Rating Scale (C-SSRS, for participants age 18 and older) or Ask Suicide Screening Questions (ASQ, for patients age 13 to 17) for all participants. Results of liver function tests, pregnancy tests, and vital signs will be recorded and tracked using a secured database.

It is expected that the total blood draw volume for this study will not exceed 16ml (for male participants) and 18ml (for female participants), using a volume of 4ml for measurement of hepatic function three times over nine weeks, and 1.5ml for serum pregnancy testing, with allowance for error in draw.

9.2 Data that are reviewed

Describe the data that are reviewed, including safety data, untoward events, and efficacy data.

Participants in this study will take the study article daily while they are enrolled in program. When they complete program, they will no longer be obliged to take the study article, nor will they be required to have weekly psychiatric evaluation, laboratory evaluation, or suicide assessments. Patients in PHP have at least one medical follow-up appointment two weeks after they complete program, and further follow-up based on the patient's needs.

During the course of the trial, we will monitor:

- New diagnoses of depression, anxiety, suicidal thoughts, suicidal ideation, self-injurious behavior and related diagnoses via chart review. Monitoring for these new diagnoses is a part of routine care of PHP
- The results of every-three-weeks liver function tests
- The results of every-three-weeks urine pregnancy tests in female participants
- Vital signs
- The results of the behavioral health surveys
- New diagnoses of abdominal pain, nausea, vomiting, headache, or fatigue regardless of relationship to diagnosis of eating disorder, though these are common problems in eating disorder treatment
- New diagnoses of jaundice, liver failure, elevated transaminases, rash, or other medical problems that are uncommon in the treatment of eating disorder.
- New diagnosis of pregnancy
- Length of participation in PHP, as patients who are experiencing good results with the study article may require a shortened length of stay in program
- Need for escalation of eating disorder or mental health care, such as need for inpatient
 hospitalization for medical stabilization of eating disorder or other medical diagnosis, need for
 residential care for eating disorder,
- Incidence of death or serious bodily harm
- Incidence of acute withdrawal from narcotic agents (expected to be zero due to preparticipation urine drug screen, though this is a serious event)

9.3 Method of collection of safety information

Describe the method by which the safety information will be collected (e.g., with case report forms, at study visits, by telephone calls and with subjects).

All patients participating in PHP receive biweekly medical visits, including comprehensive physical exam, vital signs, review of suicidal thoughts or behaviors, review of systems, and review of eating disorder symptom severity and frequency as a part of routine care in PHP. Patients also fill out the Columbia Suicide Severity Rating Scale (C-SSRS a metric assessing for the presence and severity of suicidality) or Ask Suicide Screening Questions (ASQ, a similar metric) once weekly while in care, with patients age 18 and older using the C-SSRS and patients age 13-17 using the ASQ. Participants in this study will be no different, with the notable exception of every-three-week liver function and urine pregnancy tests (assigned female at birth patients only).

Study participants' charts will be reviewed weekly while they are in program by the PI and the study coordinator for any of the above-mentioned possible new diagnoses, lab results, C-SSRS results, as well as review of all routine care detailed above. Study staff who provide direct care to participants will alert the PI and the study coordinator of any adverse events encountered during the course of routine care. The results of all safety screenings will be kept in a comprehensive, secure database and will be reviewed weekly by the study team

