7.1 Study Design

Describe and explain the study design.

This is a double-blind, randomized, placebo-controlled study. We have developed the following schedule of events. All events with a superscript $^{\circ}$ are for study purposes only and are not part of the standard of care:

	Pre-Enrollment Screening: Medical	Enrollment	Week 1	Week 2	Week 3	Week 4	Week 5	Week 6 (end of treatment	Week 8-9 (post- treatment)	Six Months
Intervention								_	>	
Initial Medical Assessment	Х									
Subsequent Medical Assessment, including comprehensive review of systems			x		x		x		х	х
Initial Psychiatry Assessment	X									
Subsequent Psychiatric Assessment, including suicidal ideation			х	х	х	х	х	х	х	х
Discussion of risks and benefits, inclusion and exclusion criteria ^o		х								
Consent/Assent ^o		Х								
\$25 Greenphire Clincardo		Х								х
Urine Drug Screen ^o		Х								
Serum Pregnancy Test (female participants)°		х								
Urine Pregnancy Test (female participants)°					х			х		
Administer Study Article ^o			Х	Х	х	Х	Х	х		
EKG	X									
AST	X				Xº			Xº		
ALT	Х				χ°			Xo		
Total Bilirubin	Х				Xº			Xº		
Direct bilirubin	Х				Xº			Xº		
Heart Rate	Х		Х	Х	Х	Х	Х	Х	Х	Х
BMI	X		Х	Х	Х	Х	Х	X	Х	Х
Height	X		Х	X	X	X	Х	X	X	Х
Weight	X		X	X	X	X	X	X	X	X
Blood Pressure	X		X	X	X	X	X	X	X	X
Temperature Adverse event monitoring ^o	Х		X	x	x	x	x	x	X	X
Suicidal Ideation Screening (ASQ			^	^	^	^	^			
for age <17or C-SSRS for age 18+)		х	Х	Х	х	Х	Х	х	Х	Х
ED-15		Х	х		х			Х	X	х
EDE-Q		Х	х		х			Х	X	Х
ABUSI°		Х	Х		х			Х	Х	Х
GAD-7		Х	х		х			Х	Х	Х
PHQ-9		Х	Х		Х			Х	X	Х
BIS/BAS°		Х	Х		Х			Х	Х	Х

Note: Medical assessments may occur in weeks 1,3 etc or 2,4 etc depending on standard of care for that patient. As long as patients are seen within a 14 day interval (2 week timeframe), the exact week intervals (1,3 or 2,4) may vary. Additionally, the 6 month follow up appointment may take place any time between 5-7 months after study enrollment ends.

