The subject will be provided with oral naltrexone or placebo weekly from the MSHMC research pharmacy. Subjects will be given one weeks' worth of medication at a time. Subjects will be randomized at enrollment to receive either study drug (naltrexone) or placebo. Participants or parents of minor participants will be provided study drug or placebo following completion of urine drug screen and consent/assent. Patients will take the medication daily while they are in programming; after completion of programming or withdrawal from the study they will no longer be given study medication. For subjects who are enrolled in child PHP and who eat meals with parents, the families may choose to administer study drug during meals at programming. For adult patients enrolled in adult programming, subjects may choose to self-administer the medication.

On their first contact with PHP, all patients in Adult PHP complete various eating disorder indices as a part of routine care, including the ED-15, PHQ-9, GAD-7, and EDE-Q. This battery of indices is repeated every 3 weeks while a patient is in programming.

For those who are enrolled in this study, they will complete their routine indices, in addition they will also complete the BIS/BAS and the ABUSI at enrollment and at weeks 1, 3, and 6 while enrolled in the study. Participants will also be asked to take the routine indices (ED-15, EDE-Q, PHQ, GAD, BIS/BAS, and ABUSI) at week 8 or 9 for a post-treatment evaluation. These will be taken in an in-person medical appointment or electronically via RedCap

6 months after enrollment, subjects will be sent copies of ED-15, EDE-Q, PHQ, GAD, BIS/BAS, and ABUSI indices either in an in-person medical appointment or via RedCap to complete. If the patient returns for medical follow-up between 5 and 7 months after enrollment, their height, weight, and body mass index will also be recorded to determine if weight restoration was maintained.

Patients in Child PHP typically complete a different inventory every three weeks as part of routine care. If a patient choses to participate in this study they will be asked to complete the same surveys as participants in Adult PHP (ED-15, GAD-7, and PHQ-9), and they will receive the same amount and type of compensation as those who already take them as part of standard of care.

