7.3.2 Treatment Regimen

Describe dose, route of administration and treatment duration. Include information about dose adjustments.

All subjects receiving study medication will receive oral naltrexone 50mg oral tablets, blinded as described above. All subjects receiving placebo will receive methylcellulose, blinded as described above. All capsules, regardless of contents, will be administered by mouth once daily, at a time of day to be chosen by the study participant.

In pediatric autism literature, doses between 0.5-2 mg/kg are described^{8,11,22,22-25}, though in adult eating disorder literature doses of 50-100mg are described^{13,14,16-18}. Food and Drug Administration labelling of oral naltrexone for treatment of alcohol use disorder and opioid receptor blockade describe an appropriate maintenance dose of 50mg per day⁷. Therefore subjects will receive 50mg of oral naltrexone a day if they are randomized to the medication group. Patients with body weight less than 25kg are excluded from the study so that no participant will exceed the maximum described pediatric dose of 2 mg/kg. Participants receiving

study article will receive 25mg of naltrexone for three days, followed by increase to study dose of 50mg/day The maximum daily dose is 50mg.

Participants will take study medication daily while they are in PHP or for six weeks total. That is, if a participant is in PHP for three weeks, they will take the study medication for the entirety of their time in PHP and then continue to take the medication for three additional weeks after discharge from PHP. If a participant is in PHP for twelve weeks—which is quite uncommon—they will only take study medication for six weeks.

For participants who complete PHP early, they will be asked to complete the same battery of surveys at 3 and 6 weeks, at weeks 8/9 for post-treatment evaluation, and at 6 months. Survey responses will be obtained via RedCAP for participants not on-site at time of survey completion.

Participants who, upon completion of the study, feel that they had significant benefit from the study article which lost upon withdrawal of the study article, are eligible for open label oral naltrexone therapy if desired. Participants will be asked at subsequent medical and behavioral health follow-up appointments if they felt they benefitted from the study article. If they feel they did, they will be offered a prescription for oral naltrexone to start at 25mg/day for three days and then 50mg a day after.

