19.1.2 Safety Monitoring

Include this section if FDA regulations apply to this study (see "WORKSHEET: Drugs (HRP-306)" and "WORKSHEET: Devices (HRP-307)". HRP-306 and HRP-307 can be accessed by clicking the Library link in CATS IRB (http://irb.psu.edu).

Indicate the process for identifying, recording and reporting adverse events.

Specify roles for adverse event recording and monitoring. Indicate each staff member's role in the adverse event reporting process. Include the following if applicable:

The **Principal Investigator** will confirm that all adverse events (AE) are correctly entered into the AE case report forms by the coordinator; be available to answer any questions that the coordinators may have concerning AEs; and will notify the IRB, FDA, sponsor and/or DSMB of all applicable AEs as appropriate. All assessments of AEs will be made by a licensed medical professional who is an investigator on the research.

The **Research Coordinator** will complete the appropriate report form and logs; assist the PI to prepare reports and notify the IRB, FDA and/or DSMB of all Unanticipated Problems/SAE's.

The **Monitor** will confirm that the AEs are correctly entered into the case report forms. The Monitor will also confirm that the adverse events are consistent with the source documents and are reported to the appropriate regulatory bodies as required.

The principal investigator assumes final responsibility for monitoring the safety of this study. Monitoring for adverse effects to medication will occur at all biweekly medical appointments as a part of routine care during PHP. If a participant develops any observable harm that is probably related to the study articles or materials the participant will be withdrawn from the study and adverse event reporting per IRB protocol will be performed.

The Principal Investigator will confirm that all adverse events (AE) are correctly entered into the AE case report forms by the coordinator; be available to answer any questions that the coordinators may have concerning AEs; and will notify the IRB, FDA, sponsor and/or DSMB of all applicable AEs as appropriate. All assessments of AEs will be made by a licensed medical professional who is an investigator on the research.

The Research Coordinator will complete the appropriate report form and logs; assist the PI to prepare reports and notify the IRB, FDA of all Unanticipated Problems/SAE's.

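### Participants who leave PHP early stay on study drug to week 6 under 7.3.2, but 9.2 and 9.3 stop requiring weekly suicide screening and chart review at program exit

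*Combined protocol and SAP*

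**What the plan says.** **Dosing after program exit.** Section 7.3.2 sets a six-week total. A participant discharged after three weeks will "continue to take the medication for three additional weeks after discharge from PHP". The 7.2 Study Procedures text says the opposite: "after completion of programming or withdrawal from the study they will no longer be given study medication". Section 9.2 takes a middle position, in which a participant who has finished the program is no longer obliged to take the drug.

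**Safety checks tied to the program.** After completion, 9.2 says of participants, "nor will they be required to have weekly psychiatric evaluation, laboratory evaluation, or suicide assessments". Section 9.3 has participants' "charts will be reviewed weekly while they are in program by the PI and the study coordinator", and describes weekly suicide screening as something done while in care. Section 19.1.2 states: "Monitoring for adverse effects to medication will occur at all biweekly medical appointments as a part of routine care during PHP"; 19.1.1 says the same.

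**Safety checks with no program limit.** The 7.1 schedule has a row for "Subsequent Psychiatric Assessment, including suicidal ideation", one for suicide screening and one for adverse event monitoring. Each is marked weekly through week 6, with no exception for program exit. Section 9.1 has the team review once a week the liver, pregnancy, vital-sign and suicide-screen results, ending with "Ask Suicide Screening Questions (ASQ, for patients age 13 to 17) for all participants". Sections 9.4 to 9.6 also describe weekly collection and review without an exit limit.

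**Early leavers specifically.** For those who finish PHP early, 7.3.2 says "they will be asked to complete the same battery of surveys at 3 and 6 weeks", again at weeks 8/9 and at six months. It does not mention suicide screening, psychiatric assessment or chart review.

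**The concern.** The sections that end weekly checks at program exit make sense if dosing also ends there. Under 7.3.2 it does not. A coordinator with a participant discharged at week 3 and still collecting capsules each week cannot tell from the protocol whether the week 4, 5 and 6 suicide screens and psychiatric assessments are required, or whether the weekly chart review should go on.

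Early exit is planned for: 7.3.2 gives it as a worked example, and 19.1.1 provides for emailing the week 6 measures to participants who have already completed PHP. Participants are aged 13 to 25. Section 10.0 lists depression and mood changes as risks of naltrexone, and notes that self-injury has occasionally worsened in the pediatric autism literature. Two suspension criteria in 9.8 and 18.7, psychiatric hospitalization for suicidal ideation and any other serious psychiatric condition possibly related to the drug, depend on the team learning of such events. If 9.2 and 9.3 are followed as written, the routine that would pick them up becomes optional while the participant is still exposed.

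**Working it through.** The protocol gives no figure of its own to reproduce. The check sets the sections side by side and counts weeks.

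**Step 1. What each section implies for a participant who exits before week 6**

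| Item | 7.3.2 | 7.2 Study Procedures | 9.2 | 9.3 | 7.1 schedule |
|---|---|---|---|---|---|
| Study drug after exit | continues to week 6 | not given | not obligatory | – | weeks 1–6 |
| Weekly suicide screen after exit | not mentioned | – | not required | described only while in care | weeks 1–6 |
| Weekly psychiatric assessment after exit | not mentioned | – | not required | – | weeks 1–6 |
| Weekly chart review after exit | not mentioned | – | – | limited to time in program | – |
| Three-weekly liver test | not mentioned | – | listed as monitored | every three weeks | weeks 3 and 6 |

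The first row is a direct contradiction: drug cannot be both continued and no longer given. The next three rows follow from it, because 9.2 and 9.3 are written for a participant who is no longer dosed.

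**Step 2. Dosing weeks without a required weekly screen or chart review**

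Inputs: six dosing weeks (7.3.2) and exit at the end of week k. Uncovered weeks = 6 − k.

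| Exit week k | 6 − k | Share of dosing period |
|---|---|---|
| 2 | 4 | 4/6 = 67% |
| 3 (protocol's example) | 3 | 3/6 = 50% |
| 4 | 2 | 2/6 = 33% |
| 5 | 1 | 1/6 = 17% |

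In the week 3 example this is 3 × 7 = 21 daily doses. The medical visit that 9.2 expects two weeks after the program falls at week 3 + 2 = 5, inside that stretch. The surveys inside it are those at week 6.

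**Step 3. How many participants**

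The documents do not give the share who leave before week 6. The 7.2 Duration of Participation text puts the average stay at about 8 weeks, and 7.3.2 calls 12 weeks quite uncommon. A mean does not fix the share below 6, but early leavers are probably a minority. As an illustration only, assume 10% to 30% of the 60 participants leave at week 3:

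- Participants: 60 × 0.10 = 6 to 60 × 0.30 = 18.
- Uncovered dosing weeks: 6 × 3 = 18 to 18 × 3 = 54.
- Planned dosing weeks: 60 × 6 = 360, so 18/360 = 5% to 54/360 = 15%.

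**The case against.** The best reply is that nothing here is forbidden. Section 9.2 says the weekly assessments are not required, and 9.3 says what happens in program without ruling anything out afterwards. A team that carries out the whole 7.1 schedule breaches neither. A reader might infer that staff cannot comply with both sets of sections. For monitoring that does not follow; only the dosing statements are truly incompatible.

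A reader might also infer that the week 6 liver test lapses at exit. The documents do not support that. The 9.2 sentence concerns weekly evaluations, whereas study liver tests are three-weekly. The list in 9.2 keeps them for the course of the trial, 7.1.2 orders them every three weeks for study participants without a program limit, and 15.1 names a six-week liver test as study-specific. A line of confirmation is enough.

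Other backstops are real:

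- weekly dispensing in clinic with return of unused capsules (7.3.4, 7.3.6.1);
- at least one medical visit two weeks after exit (9.2), with frequent appointments after PHP described in 7.1.2;
- week 6 surveys that include depression and urge to self-harm;
- a study-only adverse event row in 7.1;
- weekly review of safety results in 9.1 and in the last sentence of 9.3.

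These reduce the gap. They do not close it. Dispensing is not described as a safety check, and a weekly review of results does not order the screen that would produce them. None makes weekly suicide screening required after exit.

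Two further inferences go too far. Section 9.2 remarks that good responders may need shorter stays, which might suggest that uncovered weeks would gather in the naltrexone arm. That presupposes efficacy, and the protocol gives no exit data by arm. A reader might also extend the point to withdrawn participants, but 9.8 and 18.7 refer to study participants without excluding those who have withdrawn.

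**Conclusion.** The point holds as a conflict of text with a safety consequence. Section 7.3.2 continues study drug after early exit; the 7.2 Study Procedures text and 9.2 assume that it stops or is optional. On that assumption 9.2 and 9.3 let required weekly psychiatric and suicide assessment, and weekly chart review, end at exit, against a 7.1 schedule that runs psychiatric assessment and suicide screening to week 6.

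For each early leaver the size is exact: 6 − k of 6 dosing weeks, or half the treatment period in the protocol's own example. For the trial as a whole it is unknown and probably involves a minority; the 5% to 15% of dosing weeks above rests wholly on the assumed 10% to 30% exit share at week 3. The conclusion also assumes that 7.3.2, the most specific text on early leavers, states the intended dosing rule. If dosing were meant to end at exit, the on-drug gap would disappear, but 7.3.2 would then have to be rewritten. The protocol should be corrected either way.

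**What to change.** 1. Settle dosing first. Bring the 7.2 Study Procedures text and the opening of 9.2 into line with 7.3.2, so that study article continues to a six-week total regardless of program status.
2. In 9.2, state that the weekly suicide screening and psychiatric assessment in the 7.1 schedule continue for as long as study article is taken, and confirm that the three-weekly liver tests, including week 6, do too.
3. In 9.3, change the period of weekly chart review from time in program to the end of study article.
4. In 19.1.1 and 19.1.2, apply adverse-effect monitoring to the whole dosing period rather than to PHP appointments only.

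The cost is protocol wording and brief extra coordinator time: one chart check and one suicide screen per post-discharge dosing week, with the screen done at the weekly dispensing contact already planned. Under the illustrative range above that is 18 to 54 of each over the whole trial. The psychiatric assessments need clinician time, but 7.1 already schedules them. No contact is added beyond the 7.1 schedule and weekly dispensing.
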